3.2.2.2 Part B

The primary endpoint of Part B, ie, sNfL levels at Week 96 relative to baseline, will be analyzed using the same statistical methods described for the primary endpoint of Part A (see [Section 3.2.2.1](#)) for descriptive purpose only. Only data collected on or before IMP discontinuation will be included in the MMRM model. Plots of geometric mean ratios of sNfL levels relative to baseline in each treatment group with 90% CIs over time will be provided for better visualization.

3.2.3 Sensitivity analysis for primary endpoint in Part A

[REDACTED]

3.2.4 Supplementary analyses

Participants who permanently discontinue study intervention, including those whose background DMT is permanently modified, will be encouraged to remain in the study or to attend a safety follow-up visit within 2 weeks following discontinuation of study intervention. The sNfL levels collected after the discontinuation of study intervention or permanently modified the background DMT will be included in a supplementary analysis for the primary endpoint in Part A to assess the efficacy of SAR443820 compared to placebo in an intention-to-treat (ITT) setting, ie, the assessment of the treatment policy strategy, using mITT population. The same MMRM model on log-transformed sNfL levels as specified in [Section 3.2.2.1](#) for the main analysis of the primary endpoint in Part A will be applied. For participants who withdraw from the study before Week 48, sNfL levels will be missing after the study discontinuation. Missing data will be handled by MMRM under the missing at random (MAR) assumption.

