Based on in vitro results, SAR443820 is mainly metabolized by CYP3A4. A [REDACTED] in [REDACTED] was observed in the presence of [REDACTED] in a drug-drug interaction study. Based on PBPK modeling, administration of potent CYP3A4 inhibitors are [REDACTED]. Administration of strong CYP3A4 inducer is predicted to decrease the SAR443820 AUC. Therefore, concomitant medications or substances that are strong or moderate inhibitors or strong inducers of CYP3A4 (Appendix 10, Section 10.10, [Table 9](#)) are not allowed within the specific wash out period before the Screening Visit and for the duration of Part A and Part B.

In Part A, any modifications of SOC therapy will result in participant discontinuation from the IMP. This includes stopping, changing the dose of allowed SOC DMTs, or switching to another allowed SOC DMT, or switching to a prohibited DMT (per exclusion criterion [E 12](#)). In Part B, changes to dose of allowed DMTs or switching to another allowed DMT will be permitted.

The use of any live vaccine is prohibited within 14 days before the Screening Visit and during study duration.

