7.1 DISCONTINUATION OF STUDY INTERVENTION

7.1.1 Permanent discontinuation

Compliance with and continuation of the study intervention is encouraged, while maintaining the safety of study participants and integrity of the study. In certain instances, it may be medically necessary for a participant to permanently discontinue study intervention.

In case of the events listed below, permanent discontinuation of the IMP is mandatory (this list is not intended to be exclusive):

- The Investigator or Sponsor determines it is in the best interest of the participant.
- Occurrence of AEs or any other medical condition that, in the opinion of the Investigator or Sponsor, may jeopardize the participant's safety or data integrity. These include, but are not limited to, abnormal livers tests and meeting the stopping criteria.
- Noncompliance with the protocol, dosing regimen and visits including switching DMT or taking a prohibited DMT in Part A or Part B.
- Pregnancy of a female participant.
- Occurrence of convulsions.

Any abnormal laboratory value or ECG parameter will be immediately rechecked for confirmation after 24 hours before making a decision regarding permanent discontinuation of the IMP for the concerned participant.

Handling of participants after permanent intervention discontinuation

If a participant is withdrawn from study intervention permanently, the Sponsor will be notified within 2 business days and the date and reason(s) for the withdrawal will be documented by the Investigator in the appropriate pages of the eCRF when considered as confirmed.

Participants will be followed up according to the study procedures specified in this protocol up to study completion, or up to recovery or stabilization of any AE to be followed up as specified in this protocol, whichever comes last.

If possible, and after the definitive discontinuation of intervention, the participants will be assessed using the procedure normally planned for the last treatment day with the IMP including a PK sample. Details are provided in the SoA ([Section 1.3](#)). All cases of definitive intervention discontinuation must be recorded by the Investigator in the appropriate pages of the eCRF when considered as confirmed.

All cases of permanent intervention discontinuation must be recorded by the Investigator in the appropriate pages of the eCRF when considered as confirmed.

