2 ANALYSIS POPULATIONS

The following populations for analyses are defined.

Table 3 - Populations for analyses

Population	Description
Screened	All participants who signed the ICF.
Randomized	All participants from screened population who have been allocated to a randomized intervention by IRT regardless of whether the intervention was received.
Exposed	All screened participants who take at least 1 dose of study intervention.
Randomized and treated	All randomized participants who take at least 1 dose of study intervention. Participants will be analyzed according to the intervention allocated by randomization.
Intent-to-treat (ITT)	All randomized participants. Participants will be analyzed according to the intervention allocated by randomization.
Modified ITT (mITT)	All participants from the ITT population who take at least 1 dose of study intervention and with an evaluable primary endpoint. The primary endpoint is evaluable when the following conditions are met: 
• The participant has a baseline and at least 1 post-baseline sNfL assessment before IMP discontinuation and before permanent modification of the background DMT.• Participants will be analyzed according to the intervention allocated by randomization.
Safety	All randomized participants who take at least 1 dose of study intervention. Participants will be analyzed according to the intervention they actually received.
Pharmacokinetic (PK)	All randomized and treated participants (safety population) with at least 1 post-baseline PK result with adequate documentation of dosing and sampling dates and times. Participants will be analyzed according to the intervention they actually received.

Abbreviations: DMT = disease modifying therapy; ICF = informed consent form; IRT = interactive response technology; sNfL = serum neurofilament light chain

Participants exposed to study intervention before or without being randomized will not be considered as randomized and will not be included in any analysis population. The safety experience of these participants will be reported separately.

Randomized participants for whom it is unclear whether they took the study intervention will be considered as exposed and will be included in the safety population as randomized.

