PPMS), visit (Weeks 12, 24, 36, 48), treatment-by-visit interaction, log-transformed baseline sNfL levels and log-transformed baseline sNfL levels-by-visit interaction. An unstructured covariance structure will be used to model the within-subject errors. The Kenward-Roger (1) approximation will be used to estimate denominator degrees of freedom and adjust standard errors. Missing data will be handled by MMRM under the missing at random (MAR) assumption. The geometric mean ratios of sNfL levels at Week 48 relative to baseline in each treatment group, as well as the ratio of the geometric mean ratios under treatment with SAR443820 compared to placebo will be estimated (point estimates and 2-sided 90% confidence intervals [CI], respectively) from the MMRM model using weights for each stratum equal to the overall proportion of participants in each stratum (ie, “population weight”) through exponentiated least squared means and exponentiated least squared means differences. Plots of geometric mean ratios of sNfL levels relative to baseline in each treatment group with 90% CIs over time will be provided.

If this MMRM model fails to converge, the following variance-covariance structures will be tested in this order:

- Heterogeneous Toeplitz
- Heterogeneous AR(1)
- Heterogeneous CS
- Toeplitz
- AR(1)
- CS.

The first (co)variance structure yielding convergence will be used as the primary analysis. When a variance-covariance structure other than unstructured is used, the denominator degree of freedom will be estimated using the between within method (DDFM=BW in SAS PROC MIXED) (2)

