3.3.2 Main analytical approach

All secondary efficacy endpoints in Part A and Part B will be analyzed using the randomized and treated population. Participants who permanently discontinue the IMP or permanently modify the background DMT will be asked and encouraged to stay in the study for the remaining visits. In this case, all measurements collected after the treatment status change during the planned treatment periods will be included in the analysis.

Categorical endpoints with count data

Categorical endpoints with count data include:

Part A

- Average number of new gadolinium- (Gd-) enhancing T1-hyperintense lesions per scan from randomization to Week 48
- Annualized rate of new/enlarging T2-hyperintense lesions from randomization to Week 48
- Annualized relapse rate (ARR) of RMS population (relapsing SPMS and RRMS) from randomization to Week 48

Part B

- Number of new gadolinium- (Gd-) enhancing T1-hyperintense lesions from Week 48 to Week 96
- Annualized rate of new/enlarging T2-hyperintense lesions from Week 48 to Week 96
- ARR of RMS population (relapsing SPMS and RRMS) from randomization to Week 96

A negative binomial regression model with robust variance estimation will be used to analyze these categorical endpoints with count data. The robust variance can be estimated by specifying the participant identifier in the repeated statement using SAS PROC GENMOD (version 9.4 or later).

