3.4.2 Main analytical approach

All tertiary efficacy endpoints in Part A will be analyzed using the randomized and treated population. All measurements collected after the treatment status change during the planned treatment period for participants who discontinue the IMP or permanently modify the background DMT will be included in the analysis.

Tertiary endpoints are all continuous endpoints. Summary statistics including mean, standard deviation, median, interquartile range (Q1, Q3), minimum, and maximum will be provided at scheduled visits in Part A. Only participants with baseline and at least one post-baseline assessment will be summarized. A similar MMRM approach as described for the primary endpoint of Part A in [Section 3.2.2.1](#) will be used, except that the log-transformed baseline sNfL levels will be replaced by the baseline values of the corresponding endpoint. Appropriate transformation will be used if necessary (eg, log-transform). Plots of least squares means (\pm standard error) over time will be provided. Plots of mean (\pm SE) and/or mean change (\pm SE) over time will also be provided.

No sensitivity or subgroup analyses will be conducted.

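### The supplementary Week 48 sNfL analysis is labelled treatment policy but is run in mITT, which drops participants whose IMP stop or DMT change came before their first post-baseline sample

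*SAP*

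**What the plan says.** SAP 3.2.4 (Supplementary analyses) brings back the sNfL values that the primary analysis discards, namely those taken after IMP is stopped or background DMT is permanently modified. It uses the same MMRM as the main analysis. The stated aim is to assess the drug "in an intention-to-treat (ITT) setting, ie, the assessment of the treatment policy strategy, using mITT population".

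SAP 2, Table 3, admits a treated participant to mITT only with a baseline value and "at least 1 post-baseline sNfL assessment before IMP discontinuation and before permanent modification of the background DMT". Protocol 9.1, Table 6, sets the same condition. The model in SAP 3.2.2.1 has "visit (Weeks 12, 24, 36, 48), treatment-by-visit interaction", so Week 12 is the first post-baseline visit that it uses.

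On follow-up after stopping IMP, Protocol 7.1.1 says: "Participants will be followed up according to the study procedures specified in this protocol up to study completion". Protocol 6.8 links the two intercurrent events: "In Part A, any modifications of SOC therapy will result in participant discontinuation from the IMP".

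For the other efficacy endpoints the SAP combines post-event data with a wider population. SAP 3.3.2 states: "All secondary efficacy endpoints in Part A and Part B will be analyzed using the randomized and treated population", and adds that "all measurements collected after the treatment status change during the planned treatment periods will be included in the analysis". SAP 3.4.2 does the same for the tertiary endpoints: "All tertiary efficacy endpoints in Part A will be analyzed using the randomized and treated population".

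**The concern.** A treatment-policy estimate should not depend on whether or when the intercurrent event happened. Here it does. The event can decide whether a participant is analysed at all, because mITT was built for the hypothetical estimand, which uses only pre-event data. Those who give one qualifying sample and then stop keep all their later values. Those who stop before that sample lose all of theirs. The analysis therefore follows treatment policy only for events after the first post-baseline sample.

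Two things are at stake. First, the result would be reported as a treatment-policy estimate when it is conditioned on a post-randomization fact. If early stopping differs by arm, randomization no longer fully protects the comparison. Protocol 2.3.1 lists drug-induced liver injury as an identified risk, so a difference between arms is possible, although no rate is given. Second, this is the only readable analysis of the Part A primary endpoint in the overall population that tests how far the result depends on the hypothetical strategy. It omits the earliest stoppers, who have had the least exposure.

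**Working it through.** **1. Who is excluded.** Take a treated participant who stops IMP at Week 8, remains in follow-up and gives sNfL at Weeks 12, 24, 36 and 48.

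- The inclusion sentence in SAP 3.2.4 covers all four values, since all were collected after discontinuation.
- mITT (SAP 2) needs at least one of them to precede discontinuation. None does, so the participant is out.
- A sample at an early discontinuation visit does not help if it is taken after IMP was stopped.
- MMRM under MAR does not repair this. It deals with missing visits of participants in the model, not with observed values of people removed from the data set.

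**2. The plan's own figures.** SAP 4 gives N = 168 with 17% dropout and an upper 90% confidence limit below 0.90 for a 30% reduction (GMR 0.70).

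- Evaluable: 168 × 0.83 = 139.4. In reverse, 139/0.83 = 167.5, which rounds up to 168, so N and dropout agree.
- Largest log half-width compatible with the limit: ln(0.90/0.70) = 0.2513.
- The SD in Table 7 is redacted, so the interval itself cannot be reproduced. The point made here does not dispute it.

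**3. Size of the shift.** The documents give neither the share stopping before Week 12 nor the share who then stay, so both are assumed:

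- p = share of the SAR443820 arm stopping before the first sample
- r = share of those who give later sNfL
- GMR 0.70 in everyone else
- no drug effect in early stoppers, and placebo early stoppers like other placebo participants

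The weight of early stoppers among participants with data is s = p·r/(1 − p + p·r). The GMR in the wider set is exp[(1 − s)·ln 0.70], with ln 0.70 = −0.3567. The log shift from mITT is s × 0.3567.

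| p (of 84) | r | s | GMR, wider set | Log shift | Share of 0.2513 |
|---|---|---|---|---|---|
| 4.25% (3.6) | 1 | 0.0425 | 0.711 | 0.015 | 6% |
| 4.25% (3.6) | 0.5 | 0.0217 | 0.705 | 0.008 | 3% |
| 5% (4.2) | 1 | 0.0500 | 0.713 | 0.018 | 7% |
| 5% (4.2) | 0.5 | 0.0256 | 0.706 | 0.009 | 4% |
| 10% (8.4) | 1 | 0.1000 | 0.725 | 0.036 | 14% |
| 10% (8.4) | 0.5 | 0.0526 | 0.713 | 0.019 | 7% |
| any | 0 | 0 | 0.700 | 0 | 0% |

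The 4.25% rows tie p to the plan: 17% × 12/48 = 4.25%, assuming that IMP stopping is as frequent as the anticipated dropout and is spread evenly over 48 weeks. In every row the mITT estimate stays at 0.700.

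**4. What this does not show.** The table measures dilution of the effect. It does not measure bias from early stopping that differs by arm in frequency or prognosis. That would need assumptions about how early stoppers' sNfL differs from the rest, and the documents give no basis for them.

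**The case against.** The strongest reply concerns weight, not the text. The estimate moves only if early stoppers stay and give later samples, and the documents are mixed on that. Protocol 7.2 and SAP 3.2.4 offer either continued participation or a single safety visit. Protocol 4.1 describes an early discontinuation visit within 2 weeks. Protocol 2.3.1 says participants leave the study on the basis of ALT levels, whereas 7.1.1 and 7.1.2 describe stopping study intervention with continued follow-up; those passages need reconciling. If liver-related stoppers leave the study, they contribute nothing to the MMRM in either population. This limits the size, as the r = 0 row shows, but does not make the population fit the label.

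Other points stand in part:

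- mITT asks for any post-baseline assessment, not specifically a Week 12 one. Unscheduled samples might count, and the window tables are redacted. The number excluded cannot be read from the documents.
- SAP 3.3.2 and 3.4.2 do not use the term treatment policy, although keeping all post-event data amounts to that strategy for IMP discontinuation and DMT changes.
- Early stoppers' sNfL appears to enter the tertiary analysis by MS subtype, but SAP 3.7.2 refers NfL back to Section 3.2, so this is not certain.
- The direction of the shift follows from assuming no effect in early stoppers.

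It can also be said that holding mITT fixed isolates the change in intercurrent-event handling, and that the population is openly named. That is defensible, but then the ITT and treatment-policy description has to go. SAP 3.2.3 is redacted and might hold a related check; it would not correct the wording of 3.2.4.

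**Conclusion.** The concern holds. SAP 3.2.4 claims a treatment-policy assessment in a population whose entry condition depends on the intercurrent events. That conclusion comes from the text of SAP 2 and 3.2.4 alone and needs no assumption.

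The consequence is likely to be small. With 5% to 10% early stopping in the SAR443820 arm and half to all of those participants sampled later, the log shift is 0.009 to 0.036, or about 4% to 14% of the largest half-width compatible with the plan's precision target. These sizes rest on assumed stopping and retention rates, GMR 0.70 on drug and no effect in early stoppers. Any bias from unequal stopping between arms is not quantified. The primary analysis is untouched. The point should be fixed because the analysis does not estimate what its label says and the repair is cheap.

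**What to change.** In SAP 3.2.4, replace the reference to the mITT population with: 'using all randomized and treated participants with a baseline and at least one post-baseline sNfL value, regardless of IMP discontinuation or background DMT modification'. Keep the same MMRM. Describe the result as treatment policy in treated participants, not as an ITT setting, since ITT in SAP 2 means everyone randomized.

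Add a table by arm showing how many treated participants mITT excludes because an event preceded their first post-baseline sample, and how many of them gave later sNfL.

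This brings the analysis into line with the randomized and treated population of SAP 3.3.2 and 3.4.2. Some selection remains, because a post-baseline value is still needed. If the sponsor prefers to keep mITT, the minimum is to drop the ITT and treatment-policy label and report the same counts.

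The cost is one SAP sentence with its label, one analysis-set flag and one count table. No new data are needed. The treatment-policy estimate may come out slightly less favourable to the drug.

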7.2 PARTICIPANT DISCONTINUATION/WITHDRAWAL FROM THE STUDY

- A participant may withdraw from the study at any time at his/her own request or may be withdrawn at any time at the discretion of the Investigator for safety, behavioral or compliance reasons.
- At the time of discontinuing from the study, if possible, an early discontinuation visit should be conducted, as shown in the SoA. See the SoA for data to be collected at the time of study discontinuation and follow-up and for any further evaluations that need to be completed.
- If the participant withdraws consent for disclosure of future information, the Sponsor may retain and continue to use any data collected before such a withdrawal of consent.
- If a participant withdraws from the study, he/she may request destruction of any samples taken and not tested, and the Investigator must document this in the site study records.

For Part A and Part B, if a participant no longer wishes to take the IMP, they will be encouraged to remain in the study or to attend a safety follow-up visit within 2 weeks following discontinuation of IMP.

NOTE: No IMP reconciliation is expected at the “Safety Follow-up” visit.

The Investigators should discuss with them key visits to attend. The value of all their study data collected during their continued involvement will be emphasized as important to the public health value of the study.

Participants who withdraw from the study intervention should be explicitly asked about the contribution of possible AEs to their decision, and any AE information elicited must be documented.

All study withdrawals should be recorded by the Investigator in the appropriate screens of the eCRF and in the participant's medical records. In the medical record, at least the date of the withdrawal and the reason should be documented.

In addition, a participant may withdraw his/her consent to stop participating in the study. Withdrawal of consent for intervention should be distinguished from withdrawal of consent for follow-up visits and from withdrawal of consent for non-participant contact follow-up, eg, medical record checks. The site should document any case of withdrawal of consent.

Participants who have withdrawn from the study cannot be rerandomized/reallocated (treated) in the study. Their inclusion and intervention numbers must not be reused.

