1 INTRODUCTION

1.1 STUDY DESIGN

Study ACT16753 is a Phase 2, randomized, double-blind, placebo-controlled, 2 parallel-arm study evaluating the effect of SAR443820 on serum neurofilament light chain (sNfL) levels in participants with multiple sclerosis, followed by an open-label, long-term extension period.

The study consists of 2 parts (A and B) as follows:

Part A is a 48-week, double-blind, placebo-controlled part, preceded by a screening period of up to 4 weeks before Day 1.

- The screening period will be up to 4 weeks and is designed to evaluate suitability for participation in the study in terms of MS diagnosis, clinical status based on EDSS, and safety screening evaluations. No IMP will be administered in this period.
- The double-blind treatment period will have a total duration of 48 weeks for each participant and will include the following:
 - Participants will be randomized at 1:1 ratio to receive SAR443820 20 mg QD (n = 84) or matching placebo QD (n = 84).
 - Randomization will be stratified by MS clinical subtypes (ie, RRMS, SPMS, or PPMS) in order to ensure a balance between the treatment and placebo arms within each MS clinical subtype. Participants will attend in-clinic study assessments at baseline (Day 1) and Weeks 2, 6, 12, 24, 36, and 48.

All participants who successfully completed Part A will be offered to rollover to Part B.

Participants who discontinue IMP during Part A, or who choose not to enter Part B will have their early discontinuation or safety follow-up visit, respectively, up to 2 weeks after the last dose of IMP.

Part B is an open-label, long-term extension of Part A. Part B starts from the end of Part A (Week 48) and continues up to Week 96.

- The assignment of participants to study intervention in Part A will remain double-blinded during Part B unless there is medical need to unblind the study intervention assignment.
- All participants will receive 20 mg QD SAR443820 in Part B.
- Participants will attend in-clinic study assessments at Weeks 52, 72, and 96 (and Week 48 which is the last visit of Part A and first visit of Part B); Week 50, 54, 56, 58, 60, 62, 64, 66, 68, 70, 76, 80, 84, 88, 92 visits for liver chemistry only may be conducted at local labs where available.

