4 SAMPLE SIZE DETERMINATION

Sample size calculations were performed to ensure reasonable accuracy for the estimation of the ratio of the SAR443820 arm sNfL geometric mean relative to the placebo arm sNfL geometric mean. The width (when a GMR of █ is observed, which corresponds to a 30% reduction relative to placebo) of the 2-sided 90% CI, using a coverage correction to ensure coverage probability of █%, is displayed for various sample sizes in [Table 7](#):

Table 7 - Sample size determination

N	Log-transformed data			Corresponding geometric mean ratio (GMR)					
	Difference in means	Standard deviation (SD)	90% confidence interval (CI) half width*	Lower limit	Upper limit	GMR	Lower limit	Upper limit	Total width (asymmetric)
█	█	█	█	█	█	█	█	█	█

(*): with a coverage probability (probability that the observed interval will be no longer than the specified width) of 90%.

For an observed █ reduction relative to placebo, a sample size of 168 participants (to account for an anticipated 17% dropout rate) will provide an upper limit below 0.90 (10% of reduction) for the 2-sided 90% CI, which is deemed sufficient.

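### The treatment-policy analysis of Week 48 sNfL fills in study leavers with a missing-at-random model that ignores being off drug, so it is pulled towards the primary hypothetical estimand

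*SAP*

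**What the plan says.** SAP 3.2.4 adds sNfL values collected after IMP discontinuation or a permanent change of background DMT, and describes the result as "ie, the assessment of the treatment policy strategy, using mITT population". It reuses the MMRM of SAP 3.2.2.1 unchanged. The terms are treatment, MS clinical subtype, visit, treatment by visit, baseline log sNfL and baseline by visit; there is no on/off-IMP term. For study leavers it says "For participants who withdraw from the study before Week 48, sNfL levels will be missing after the study discontinuation", followed by "Missing data will be handled by MMRM under the missing at random (MAR) assumption".

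The primary analysis (SAP 1.2.1, Table 2, and 3.2.2.1) fits the same model under the same assumption, but drops all data after either intercurrent event. The two analyses therefore differ only through off-drug or post-DMT-change values that are actually collected.

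The documents give mixed signals on how many such values there will be:
- Protocol 7.1.1 has participants who stop IMP permanently followed until they complete the study.
- Protocol 7.2 says of participants who no longer wish to take IMP that "they will be encouraged to remain in the study or to attend a safety follow-up visit within 2 weeks following discontinuation of IMP", and SAP 3.2.4 repeats that choice.
- Protocol 2.3.1, Table 1, speaks of ALT results leading to discontinuation from the study itself.

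**The concern.** A treatment-policy effect asks what Week 48 sNfL would be whatever happened to IMP or DMT. Someone who has left the study takes no more IMP, so the missing value belongs to the off-drug state. Missing at random, in a model blind to that state, lets mostly on-drug participants in the same arm stand in for the leaver. If sNfL rises again after stopping, the SAR443820 arm looks better at Week 48 than treatment policy would show.

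Stopping for drug-related reasons is plausible here. Liver injury is an identified risk (Protocol 2.3.1), abnormal liver tests meeting the criteria require IMP to stop (Protocol 7.1.2), and any Part A change of DMT also ends IMP (Protocol 6.8).

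What is at stake is the value of the supplementary analysis as a check. If most stoppers leave, it will nearly reproduce the primary estimate by construction, and the agreement could be read as evidence that stopping does not matter.

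**Working it through.** **Inputs from the documents.** 168 participants randomized 1:1, so 84 per arm (SAP 1.1); a planning reduction, "which corresponds to a 30% reduction relative to placebo", that is a GMR of 0.70; and a sample size set "to account for an anticipated 17% dropout rate" (both SAP 4).

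**The plan's own figure.** 168 × 0.83 = 139.4 evaluable, and 139 / 0.83 = 167.5, which rounds up to 168. So 168 and 17% agree. The confidence limit below 0.90 cannot be reproduced because the SD is blacked out. The log half-width it implies is ln(0.90/0.70) = 0.251. The SAP gives no figure for the supplementary analysis.

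**Assumptions not in the documents.** The 17% is used as the IMP-stop rate d in each arm. Stopping falls equally after Weeks 12, 24 and 36 and is unrelated to sNfL. Stoppers not retained leave the study when they stop IMP. Off-drug sNfL returns fully to the placebo level.

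**Treatment-policy value.** ln 0.70 = −0.357. With d = 0.17 and full loss of effect, the log difference is 0.83 × (−0.357) = −0.296, so the GMR is 0.70^0.83 = 0.744.

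**What the planned model targets.** If a share r of stoppers is retained, the off-drug share among those observed at Week 48 is dr / (1 − d + dr). The MMRM then gives approximately 0.70^(1 − that share). For r = 0.5 this is 0.085 / 0.915 = 0.093, and 0.70^0.907 = 0.724. A large-sample simulation checks this (400,000 participants, baseline plus four visits, unstructured maximum likelihood, arm-by-visit means, no off-drug term, MS subtype omitted).

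| Stoppers retained | Approximation | Simulation | Treatment policy | Bias as share of log effect |
|---|---|---|---|---|
| 0% | 0.700 | about 0.70 | 0.744 | 17% |
| 25% | 0.712 | 0.713 | 0.744 | about 12% |
| 50% | 0.724 | 0.723 | 0.744 | about 8% |
| 75% | 0.734 | 0.734 | 0.744 | about 4% |
| 100% | 0.744 | about 0.744 | 0.744 | none |

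The last column uses the simulated values; for 50% it is (ln 0.744 − ln 0.723) / 0.357, about 8%. Within-person correlations of 0.5, 0.7 and 0.85 gave nearly the same results.

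**Variations.**
- Half the effect lost, none retained: the treatment-policy value is 0.70^0.915 = 0.722, against 0.70 from the model.
- Each leaver gives one off-drug value before withdrawing: the model gives 0.722 against 0.744, about half the gap.
- 25% stop IMP and 17% leave the study: treatment policy about 0.766, model about 0.725.
- Effect persists off drug: no such bias.

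**Scale.** The largest gap in the table, 0.357 − 0.296 = 0.061 on the log scale, is 0.061 / 0.251 = 24% of the planning half-width. With half retained it is about 0.028 / 0.251 = 11%.

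**The case against.** A reader might infer that leavers are simply treated as if still on SAR443820. The documents do not support that in general. SAP 3.2.4 brings collected off-drug values into the model, so the arm means, and a leaver's own earlier values, carry off-drug information. The inference is exact only when almost no stopper is retained, and Protocol 7.1.1 plans follow-up to the end. Equally, Protocol 7.2 and Table 1 in Protocol 2.3.1 mean full retention cannot be taken for granted.

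A reader might also infer that this is the only visible sNfL analysis that uses data after stopping. It is not. Change in sNfL by MS subpopulation is a tertiary endpoint, and SAP 3.4.2 analyses tertiary endpoints in all randomized and treated participants with post-stop values included. That analysis also relies on an MMRM, so it does not resolve the missing-data question.

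Other limits stand:
- SAP 3.2.3, the sensitivity analysis for the primary endpoint, is blacked out and may depart from missing at random. It cannot be judged, and 3.2.4 does not refer to it.
- The 17% is a dropout rate for sample size, not an IMP-stop rate, and complete rebound is the extreme case.
- Some stoppers will have changed DMT, and Protocol 2.1 says effective MS treatments mostly lower sNfL. Off-drug values need not follow the placebo course, so the size and even the direction of the error are not certain.
- This is a supplementary analysis in a Phase 2 estimation study, and its assumption is stated openly.

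These points limit the size of the problem. They do not bring the missing-data method into line with the stated estimand.

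**Conclusion.** The point holds as a mismatch between estimand and missing-data method in SAP 3.2.4. The estimate is pulled towards the hypothetical estimand, and this favours SAR443820 if its effect wanes off drug. Under full loss of effect and 17% stopping, the error runs from none (all stoppers retained) to 0.70 against 0.744 (none retained). It shrinks with partial rebound and disappears if the effect persists. The IMP-stop rate, retention and rebound are all assumptions.

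The primary result is not affected, and nothing here shows that it is wrong. The restriction to mITT is a separate matter; changing the population would not cure this. The point merits a change because the change is cheap, not because the trial's main conclusion depends on it.

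**What to change.** In SAP 3.2.4, before unblinding:

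1. Replace the missing-at-random sentence with multiple imputation of post-withdrawal log sNfL, drawn from participants in the same arm who stopped IMP but stayed in the study.
2. State a minimum number of retained stoppers per arm for this to be used. At 17% there would be about 0.17 × 84 = 14 stoppers per arm before any loss, so the fallback may well be needed.
3. Below that number, use one named reference-based method (for example jump-to-reference from the placebo arm) for SAR443820 leavers, and missing at random for placebo leavers. Name the method now so that no choice remains after the data are seen. State as a limitation that placebo leavers who changed DMT stay under missing at random.
4. Analyse each imputed set with the same model, combine by Rubin's rules, and report the planned MMRM result alongside, with the number of stoppers retained per arm.

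The follow-up statements in Protocol 2.3.1 (Table 1), 7.1.1 and 7.2 should also be reconciled, since retention drives the size of the problem.

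The cost is SAP wording and some programming, with no new data. The downside is a possibly wider interval and a less favourable supplementary estimate.
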